10.1.2 Financial disclosure

Investigators and sub-Investigators will provide the Sponsor with sufficient, accurate financial information as requested to allow the Sponsor to submit complete and accurate financial certification or disclosure statements to the appropriate regulatory authorities. Investigators are responsible for providing information on financial interests during the course of the study and for 1 year after completion of the study.

10.1.3 Informed consent process

- The Investigator or his/her representative will explain the nature of the study to the participant or his/her legally authorized representative and answer all questions regarding the study.
- Participants must be informed that their participation is voluntary. Participants or their legally authorized representative will be required to sign a statement of informed consent that meets the requirements of 21 CFR 50, local regulations, ICH guidelines, Health Insurance Portability and Accountability Act (HIPAA) requirements, where applicable, and the IRB/IEC or study center.
- The medical record must include a statement that written informed consent was obtained before the participant was enrolled in the study and the date the written consent was obtained. The authorized person obtaining the informed consent must also sign the ICF.
- Participants must be re-consented to the most current version of the ICF(s) during their participation in the study.
- A copy of the ICF(s) must be provided to the participant or the participant’s legally authorized representative.

A participant who is rescreened is not required to sign another ICF if the rescreening occurs within 5 days from the previous ICF signature date.

The ICF will contain a separate section that addresses the use of remaining mandatory samples or new extra samples for optional exploratory research. The Investigator or authorized designee will explain to each participant the objectives of the exploratory research. Participants will be told that they are free to refuse to participate and may withdraw their consent at any time and for any reason during the storage period. A separate consent will be required to document a participant's agreement to allow any remaining specimens to be used for exploratory research. Participants who decline to participate in this optional research will not provide this separate consent.

10.1.4 Data protection

All personal data collected related to participants, Investigators, or any person involved in the study, which may be included in the Sponsor's databases, shall be treated in compliance with all applicable laws and regulations including the GDPR (General Data Protection Regulation).

Data collected must be adequate, relevant and not excessive, in relation to the purposes for which they are collected. Each category of data must be properly justified and in line with the study objective.

Participant race and ethnicity will be collected in this study because these data are required by regulatory agencies (eg, on afro American population for the United States Food and Drug Administration (FDA) or on Japanese population for the Pharmaceuticals and Medical Devices Agency in Japan).

- Participants will be assigned a unique identifier by the Sponsor. Any participant records or datasets that are transferred to the Sponsor will contain the identifier only; participant names or any information which would make the participant identifiable will not be transferred to the Sponsor.
- The participant must be informed that his/her personal study-related data will be used by the Sponsor in accordance with local data protection law. The level of disclosure must also be explained to the participant as described in the informed consent.
- The participant must be informed that his/her medical records may be examined by Clinical Quality Assurance auditors or other authorized personnel appointed by the Sponsor, by appropriate IRB/IEC members, and by inspectors from regulatory authorities.
- When archiving or processing personal data pertaining to the Investigator and/or to the participants, the Sponsor shall take all appropriate measures to safeguard and prevent access to this data by any unauthorized third party.
- Participant data are intended to be used for the whole drug development program from collection to reimbursement.

10.1.5 Committees structure

The Study Committee will be comprised of the Principal Investigator from each site involved in the dose escalation phase, clinical team members from the Sponsor (including at least the Study Medical Manager and Global Study Manager, and experts, including the Global Safety Officer, pharmacokineticists, biostatisticians).

The Study Committee will review clinical data on a regular basis, with a review being performed at least at the end of each DL cohort, before the enrollment of new participants at the next DL, and at the end of the dose escalation phase of the study. The Study Committee in agreement with the Sponsor's Study Medical Manager will decide on whether to escalate or de-escalate to the next DL or to add alternative dose levels during Study Committee meetings based on current safety profile and tolerability, available PK information, and statistical design recommendation. Decisions regarding participant treatment and cohort expansion will be discussed and clearly documented in the discussion minutes. The Study Committee in agreement with the Sponsor's Study Medical Manager may permit the evaluation of additional DL and/or additional schedules of administration of SAR442720, depending upon the observed safety and DLT at each DL, and the safety and/or PK data observed in the ongoing Phase 1 monotherapy escalation study.

10.1.6 Dissemination of clinical study data

Sanofi shares information about clinical trials and results on publicly accessible websites, based on company commitments, international and local legal and regulatory requirements, and other clinical trial disclosure commitments established by pharmaceutical industry associations. These websites include clinicaltrials.gov, EU clinicaltrialregister (eu.ctr), and sanofi.com, as well as some national registries.

In addition, results from clinical trials in participants are required to be submitted to peer-reviewed journals following internal company review for accuracy, fair balance and intellectual property. For those journals that request sharing of the analyzable data sets that are reported in the publication, interested researchers are directed to submit their request to clinicalstudydatarequest.com.

Individual participant data and supporting clinical documents are available for request at clinicalstudydatarequest.com. While making information available we continue to protect the privacy of participants in our clinical trials. Details on data sharing criteria and process for requesting access can be found at this web address: clinicalstudydatarequest.com.

10.1.7 Data quality assurance

- All participant data relating to the study will be recorded on printed or electronic CRF unless transmitted to the Sponsor or designee electronically (eg, laboratory data). The Investigator is responsible for verifying that data entries are accurate and correct by physically or electronically signing the CRF.
- The Investigator must maintain accurate documentation (source data) that supports the information entered in the CRF.
- The Investigator must permit study-related monitoring, audits, IRB/IEC review, and regulatory agency inspections and provide direct access to source data documents.
- Monitoring details describing strategy (eg, risk-based initiatives in operations and quality such as Risk Management and Mitigation Strategies and Analytical Risk-Based Monitoring), methods, responsibilities and requirements, including handling of

noncompliance issues and monitoring techniques (central, remote, or on-site monitoring) are provided in separate study documents.

- The Sponsor or designee is responsible for the data management of this study including quality checking of the data.
- The Sponsor assumes accountability for actions delegated to other individuals (eg, Contract Research Organizations).
- Study monitors will perform ongoing source data verification to confirm that data entered into the CRF by authorized site personnel are accurate, complete, and verifiable from source documents; that the safety and rights of participants are being protected; and that the study is being conducted in accordance with the currently approved protocol and any other study agreements, ICH GCP, and all applicable regulatory requirements.
- Records and documents, including signed ICFs, pertaining to the conduct of this study must be retained by the Investigator for 25 years after the signature of the final study report unless local regulations or institutional policies require a longer retention period. No records may be destroyed during the retention period without the written approval of the Sponsor. No records may be transferred to another location or party without written notification to the Sponsor.

10.1.8 Source documents

- Source documents provide evidence for the existence of the participant and substantiate the integrity of the data collected. Source documents are filed at the Investigator's site.
- Data reported on the CRF or entered in the eCRF that are transcribed from source documents must be consistent with the source documents or the discrepancies must be explained. The Investigator may need to request previous medical records or transfer records, depending on the study. Also, current medical records must be available.

10.1.9 Study and site start and closure

The study start date is the date on which the clinical study will be open for recruitment of participants.

The first act of recruitment is the first participant first visit and will be the study start date.

The Sponsor or designee reserves the right to close the study site or terminate the study at any time for any reason at the sole discretion of the Sponsor. Study sites will be closed upon study completion. A study site is considered closed when all required documents and study supplies have been collected and a study-site closure visit has been performed.

The Investigator may initiate study-site closure at any time, provided there is reasonable cause and sufficient notice is given in advance of the intended termination.

Reasons for study termination by the Sponsor, as well as reasons for the early closure of a study site by the Sponsor or Investigator may include but are not limited to:

- For study termination:
 - Information on the product leads to doubt as to the benefit/risk ratio
 - Discontinuation of further study intervention development
- For site termination:
 - Failure of the Investigator to comply with the protocol, the requirements of the IRB/IEC or local health authorities, the Sponsor's procedures, or GCP guidelines
 - Inadequate or no recruitment (evaluated after a reasonable amount of time) of participants by the Investigator
 - Total number of participants included earlier than expected

If the study is prematurely terminated or suspended, the Sponsor shall promptly inform the Investigators, the IECs/IRBs, the regulatory authorities, and any contract research organization(s) used in the study of the reason for termination or suspension, as specified by the applicable regulatory requirements. The Investigator shall promptly inform the subject and should assure appropriate subject therapy and/or follow-up.

10.1.10 Publication policy

- The results of this study may be published or presented at scientific meetings. If this is foreseen, the Investigator agrees to submit all manuscripts or abstracts to the Sponsor before submission. This allows the Sponsor to protect proprietary information and to provide comments.
- The Sponsor will comply with the requirements for publication of study results. In accordance with standard editorial and ethical practice, the Sponsor will generally support publication of multicenter studies only in their entirety and not as individual site data. In this case, a coordinating Investigator will be designated by mutual agreement.
- Authorship will be determined by mutual agreement and in line with International Committee of Medical Journal Editors authorship requirements.

10.2 APPENDIX 2: CLINICAL LABORATORY TESTS

- The tests detailed in [Table 22](#) will be performed by the local laboratory.
- Protocol-specific requirements for inclusion or exclusion of participants are detailed in [Section 5](#) of the protocol.
- Additional tests may be performed at any time during the study as determined necessary by the Investigator or required by local regulations.
- C2+Day 15 laboratory assessments could be done remotely if needed and after discussion with the Study Medical Manager.
- Pregnancy testing. Refer to [Section 5.1](#) for screening criteria, Appendix 4 ([Section 10.4](#)) for WOCBP criteria and SoA ([Section 1.3](#)) for time points.

- Results of each test must be entered into the eCRF.

Table 22 - Protocol-required laboratory assessments

Laboratory assessments	Parameters
Hematology	Platelet count Red blood cell (RBC) count Hemoglobin Hematocrit RBC indices: Mean corpuscular volume (MCV) Mean corpuscular hemoglobin (MCH) %Reticulocytes White blood cell (WBC) count with differential: Neutrophils Bands (if available) Lymphocytes Monocytes Eosinophils Basophils, other cells
Clinical chemistry ^a	Blood urea nitrogen (BUN) Creatinine Glucose nonfasting Potassium Sodium Chloride Bicarbonate Calcium Magnesium Phosphorous Uric acid Albumin Amylase Lipase Aspartate aminotransferase (AST)/ Serum glutamic-oxaloacetic transaminase (SGOT) Alanine aminotransferase (ALT)/ Serum glutamic-pyruvic transaminase (SGPT) Alkaline phosphatase Gamma-glutamyl transferase (GGT) Total and direct bilirubin Total protein Specific gravity pH, glucose, protein, blood, ketones, bilirubin, urobilinogen, nitrite, leukocyte esterase by dipstick Microscopic examination (if blood or protein is abnormal)
Routine urinalysis ^b	Total and heart muscle (MB) component (not required for screening purposes)
CPK isoenzymes	

Laboratory assessments	Parameters
Other screening tests	
Coagulation test to include prothrombin time (PT)/international normalized ration (INR) and aPTT (or partial thromboplastin time)
 
Follicle-stimulating hormone and estradiol (as needed in women of non-childbearing potential only)^c
 
Highly sensitive blood or urine human chorionic gonadotropin (hCG) pregnancy test (as needed for women of childbearing potential)^b
 
Serology: hepatitis B surface antigen (HBsAg), hepatitis B core antibody (HBcAb), and hepatitis C virus antibody. If hepatitis C virus antibody is positive, then obtain hepatitis-C RNA
 
The results of each test must be entered into the case report form (CRF).

NOTES :

- a Concurrent elevation of AST or ALT >3 x ULN AND total bilirubin >2 x ULN or INR >1.5 in the absence of cholestasis and other causes (eg, viral hepatitis, other pre-existing or acute liver disease, or another drug capable of the observed injury), which may indicate severe drug-induced liver injury (possible Hy's law case). All events with the defined biochemical abnormalities must be reported as an SAE; and study medications should be permanently discontinued.
- b Local urine testing will be standard for the protocol unless blood testing is required by local regulation or IRB/IEC. For screening a blood test is required.
- c See Appendix 4 ([Section 10.4](#)).

Investigators must document their review of each laboratory safety report.

10.3 APPENDIX 3: ADVERSE EVENTS: DEFINITIONS AND PROCEDURES FOR RECORDING, EVALUATING, FOLLOW-UP, AND REPORTING

10.3.1 Definition of AE

AE definition

- An AE is any untoward medical occurrence in a participant or clinical study participant, temporally associated with the use of study intervention, whether or not considered related to the study intervention.
- NOTE: An AE can therefore be any unfavorable and unintended sign (including an abnormal laboratory finding), symptom, or disease (new or exacerbated) temporally associated with the use of study intervention.

Events meeting the AE definition

- Any abnormal laboratory test results (hematology, clinical chemistry, or urinalysis) or other safety assessments (eg, ECG, radiological scans, vital signs measurements), including those that worsen from baseline, considered clinically significant in the medical and scientific judgment of the Investigator (ie, not related to progression of underlying disease), eg:
 - Leading to IMP discontinuation or modification of dosing, and/or
 - Fulfilling a seriousness criterion, and/or
 - Defined as an AESI

- Exacerbation of a chronic or intermittent pre-existing condition including either an increase in frequency and/or intensity of the condition.
- New conditions detected or diagnosed after study intervention administration even though it may have been present before the start of the study.
- Signs, symptoms, or the clinical sequelae of a suspected drug-drug interaction.
- Signs, symptoms, or the clinical sequelae of a suspected overdose of either study intervention or a concomitant medication.
- “Lack of efficacy” or “failure of expected pharmacological action” per se will not be reported as an AE or SAE. Such instances will be captured in the efficacy assessments. However, the signs, symptoms, and/or clinical sequelae resulting from lack of efficacy will be reported as AE or SAE if they fulfil the definition of an AE or SAE.
- The signs, symptoms, and/or clinical sequelae resulting from lack of efficacy will be reported as AE or SAE if they fulfil the definition of an AE or SAE. Also, “lack of efficacy” or “failure of expected pharmacological action” also constitutes an AE or SAE.

Events NOT meeting the AE definition

- Any clinically significant abnormal laboratory findings or other abnormal safety assessments which are associated with the underlying disease, unless judged by the Investigator to be more severe than expected for the participant’s condition.
- The disease/disorder being studied or expected progression, signs, or symptoms of the disease/disorder being studied, unless more severe than expected for the participant’s condition.
- Medical or surgical procedure (eg, endoscopy, appendectomy): the condition that leads to the procedure is the AE.
- Situations in which an untoward medical occurrence did not occur (social and/or convenience admission to a hospital).
- Anticipated day-to-day fluctuations of pre-existing disease(s) or condition(s) present or detected at the start of the study that do not worsen.

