8.3.1 Time period and frequency for collecting AE and SAE information

All SAEs will be collected from the signing of the ICF until the follow-up visit at the time points specified in the SoA ([Section 1.3](#)).

All AE will be collected from the signing of the ICF at the time points specified in the SoA ([Section 1.3](#)).

After the signing of the ICF, but prior to initiation of study intervention, only SAEs caused by a protocol mandated intervention will be collected (eg, SAEs related to invasive procedures, such as biopsies or medication washout). Any medical occurrence that begins before the start of study intervention but after obtaining informed consent, and which is not considered an SAE caused by a protocol mandated intervention will be recorded on the Medical History/Current Medical Conditions Section of the eCRF not the AE section.

All SAEs and AESI will be recorded and reported to the Sponsor or designee immediately and under no circumstance should this exceed 24 hours, as indicated in Appendix 3 ([Section 10.3](#)). The Investigator will submit any updated SAE data to the Sponsor within 24 hours of it being available.

Investigators are not obligated to actively seek AE or SAE after conclusion of the study participation. However, if the Investigator learns of any SAE, including a death, at any time after a participant has been discharged from the study, and he/she considers the event to be reasonably related to the study intervention or study participation, the Investigator must promptly notify the Sponsor.

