9.4.3 Safety endpoint(s)

Safety endpoints including incidence and severity of AEs and SAEs and laboratory abnormalities are the primary endpoints for Part-1 and Part-3A and secondary endpoint for Part-2, Part-3B, and Part-4.

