10.3.2 Definition of SAE

If an event is not an AE per definition above, then it cannot be an SAE even if serious conditions are met (eg, hospitalization for signs/symptoms of the disease under study, death due to progression of disease).

A SAE is defined as any untoward medical occurrence that, at any dose:

- Results in death**
- Is life-threatening**

The term “life-threatening” in the definition of “serious” refers to an event in which the participant was at risk of death at the time of the event. It does not refer to an event, which hypothetically might have caused death, if it were more severe.

c) Requires inpatient hospitalization or prolongation of existing hospitalization

In general, hospitalization signifies that the participant has been detained (usually involving at least an overnight stay) at the hospital or emergency ward for observation and/or treatment that would not have been appropriate in the physician's office or outpatient setting. Complications that occur during hospitalization are AEs. If a complication prolongs hospitalization or fulfills any other serious criteria, the event is serious. When in doubt as to whether "hospitalization" occurred or was necessary, the AE should be considered serious.

Hospitalization for elective treatment of a pre-existing condition that did not worsen from baseline is not considered an AE.

d) Results in persistent disability/incapacity

- The term disability means a substantial disruption of a person's ability to conduct normal life functions.
- This definition is not intended to include experiences of relatively minor medical significance such as uncomplicated headache, nausea, vomiting, diarrhea, influenza, and accidental trauma (eg, sprained ankle) which may interfere with or prevent everyday life functions but do not constitute a substantial disruption.

e) Is a congenital anomaly/birth defect

f) Other situations:

- Medical or scientific judgment should be exercised in deciding whether SAE reporting is appropriate in other situations such as important medical events that may not be immediately life-threatening or result in death or hospitalization but may jeopardize the participant or may require medical or surgical intervention to prevent one of the other outcomes listed in the above definition. These events should usually be considered serious.

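### Adjacent bullets in the AE definition give opposite rules on lack of efficacy, so sites may differ on whether progression is reported as an AE or SAE

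*Protocol*

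**What the plan says.** Protocol 10.3.1 (Appendix 3) lists events that meet the AE definition. One bullet states that lack of efficacy, or failure of the expected pharmacological action, "per se will not be reported as an AE or SAE. Such instances will be captured in the efficacy assessments". It adds that resulting signs, symptoms or sequelae are reported if they themselves fit the definition. The next bullet repeats that sentence about sequelae and then says that lack of efficacy "also constitutes an AE or SAE".

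Three other statements in the same appendix deal with progression directly:

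- Abnormal tests and safety assessments, scans included, count as AEs when judged clinically significant, glossed as "ie, not related to progression of underlying disease" (10.3.1).
- The list of events that are not AEs includes "The disease/disorder being studied or expected progression, signs, or symptoms of the disease/disorder being studied, unless more severe than expected" (10.3.1).
- An event that is not an AE cannot be an SAE; the examples are "hospitalization for signs/symptoms of the disease under study, death due to progression of disease" (10.3.2).

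On rank, Protocol 9.4.3 says that AE and SAE incidence and severity, with laboratory abnormalities, "are the primary endpoints for Part-1 and Part-3A and secondary endpoint for Part-2, Part-3B, and Part-4". SAP 4.3 agrees. SAP Table 2, however, prints the Part-3A AE and SAE endpoint under the secondary objectives.

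**The concern.** The AE definition decides what enters the safety database. Here it answers one question both ways, in neighbouring bullets of the current text. In an oncology trial, a site may reasonably take disease progression to be the main form that lack of efficacy takes. A site that does so and follows the second bullet would enter progression as an AE, and a death from it as an SAE. A site that follows the first bullet would enter neither.

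At stake are the descriptive safety tables, which carry a primary endpoint in Part-1 and Part-3A. If practice differs between sites, rates at different dose levels or in different cohorts would partly reflect which sites enrolled there.

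**Working it through.** There is no planned figure to reproduce. The check sets the texts side by side and follows a progression event through the analysis rules.

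**1. How each text treats progression**

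| Text | Answer |
|---|---|
| 10.3.1, first lack-of-efficacy bullet | Not an AE or SAE in itself |
| 10.3.1, second lack-of-efficacy bullet | An AE or SAE, if progression is taken to be lack of efficacy |
| 10.3.1, abnormal findings | Not an AE when related to progression |
| 10.3.1, events that are not AEs | Not an AE if expected; a more severe course is left to judgement |
| 10.3.2 | Death from progression given as an example of what cannot be an SAE |

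Four of the five point the same way, and the second bullet is the outlier. The 10.3.2 statement is conditional on the event not being an AE under the preceding definition, so it takes over the conflict in 10.3.1 and does not resolve it.

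**2. Whether such an event would fall in the analysis window**

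Participants are treated until progression or another stopping reason (Protocol 4.1). The treatment-emergent period runs to 30 days after the last dose (Protocol 9.4.3.1; SAP 4.1). Progression that ends treatment would generally fall inside it.

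**3. Which tables it would enter if recorded as an AE**

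- TEAE counts, overall and by preferred term (SAP 4.3).
- SAE counts: Protocol 10.3.3 makes every Grade 4 or 5 AE serious.
- Grade 5 TEAEs. The SAP 4.3 line covers fatal TEAEs or all-cause mortality, so it is unclear whether it depends on AE status at all.
- TEAEs leading to discontinuation. Protocol 7.1.1 lists documented progression and significant AEs as separate reasons for stopping; recording progression as an AE merges them.
- Treatment-related TEAEs, if causality is left blank, because SAP 4.3 then assumes a relationship.

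SAP 4.3 has no step that identifies or removes progression terms.

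**4. What it would not enter**

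- DLTs: Protocol 4.1.1 excludes events due to disease progression.
- MTD and RP2D: Protocol 4.1 applies the same exclusion to the AEs considered, for both Part-1 and Part-3A.
- The deaths table: SAP 4.3 counts deaths by on-treatment and post-treatment period, whatever their AE status.

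**5. Scale**

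The documents do not say how many participants will progress in the window or how sites will read the bullets, so no shift can be calculated. What follows from the planned numbers is the weight of one participant in a table row, 100/N percentage points:

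- Part-3B, N = 40: 100/40 = 2.5.
- Each Part-2 cohort, N = 20: 100/20 = 5.
- A Part-3A dose level of 3 to 6: 100/6 = 16.7 to 100/3 = 33.3.

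This is sensitivity per participant, not an estimate of the effect. The any-TEAE row moves only if the participant has no other TEAE.

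**The case against.** The strongest reply is that the protocol never equates lack of efficacy with progression. It treats progression separately, and each time excludes it unless it is more severe than expected. A site that looks up progression finds a specific rule. Divergence requires a site to make the equation, follow the second bullet and pass over the exclusions. Progression terms would also be visible by preferred term, and no hypothesis test rests on AE counts.

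Much of this stands. It makes divergent reporting a risk, not an established fact, and limits the harm to descriptive tables. It does not remove the contradiction. The exclusion list covers only expected progression, 10.3.2 depends on 10.3.1, and the SAP does not say what to do with progression terms once seen. The amendment 04 summary of changes records that the AE definition was corrected for an oncology study, but not which bullet was intended.

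A reader might also infer a parallel conflict in Protocol 8.3.1, which says "All AE will be collected from the signing of the ICF at the time points specified in the SoA" and then that before first dose "only SAEs caused by a protocol mandated intervention will be collected". The documents do not support that firmly. The text can be read as a general rule followed by a qualifier, and pre-dose events lie outside the treatment-emergent window. The SAP 4.3 description of pre-treatment AEs should stay: without it, the protocol-caused SAEs still collected in that period would go unreported.

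**Conclusion.** The contradiction is real and is in the current text. The second bullet conflicts with the first, with the exclusion list in 10.3.1 and with 10.3.2. It could shift descriptive TEAE, SAE, Grade 5 TEAE and discontinuation counts in every part. By Protocol 9.4.3 and SAP 4.3, AE and SAE incidence is primary in Part-1 and Part-3A and secondary in the others.

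The conclusion assumes that some sites will read progression as lack of efficacy; the documents neither say nor rule this out. A reader might infer that progression is already handled differently across sites, or that the AE rate could move by the whole share of participants who progress. Neither is supported. No site practice is documented, no progression rate is given, and the extreme case needs every site to override the specific exclusions. Nor does the problem reach dose selection.

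**What to change.** 1. Delete the second lack-of-efficacy bullet in Protocol 10.3.1. Its sentence on sequelae is already in the first, so nothing else is lost, and the definition then agrees with the exclusion list and 10.3.2. The sponsor should confirm that this is the intended rule.
2. Tell sites which rule applies, and query any disease-progression AE terms already entered.
3. State in SAP 4.3 how remaining progression terms and deaths from progression are handled in the TEAE, SAE and Grade 5 tables. One workable form is to list them separately, outside those tables, with progression deaths counted in the deaths table. The Grade 5 line should count either fatal TEAEs or all-cause mortality, not both under one label.
4. Reconcile the rank of the Part-3A AE endpoint in SAP Table 2 with SAP 4.3 and Protocol 9.4.3.

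The cost is a minor protocol edit needing IRB/IEC approval before implementation (Protocol 10.1.1), a short SAP edit, a site communication and some data queries. No participants or visits are added. The work is best finished before database lock.
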